5 DONOR SELECTION AND PROCEDURES

Donors will undergo standard of care procedures for mobilization and leukapheresis. They will be asked to sign consents per standard of care procedures. There will be no research procedures for the donor.

5.1 Mobilization Therapy for Peripheral Blood Leukapheresis

Following screening and enrollment, the donor will receive mobilization therapy per institutional guidelines with daily G-CSF. Recommended dose of G-CSF is 16 mg/kg/day subcutaneously (rounded off to the nearest vial size of either 300 or 480 μ g). Donors will receive G-CSF once a day for 5 days, with the leukapheresis occurring on day 5. If needed, an additional dose of G-CSF and leukapheresis procedure may occur on day 6 if needed to meet cell dose requirements. Plerixafor (mozibil) may also be given per institutional standards to increase peripheral blood stem cells prior to leukapheresis procedure.

Target post-selection cell dose is 20 x 10⁶ cells/kg with a CD3 cell dose of less than or equal to 3 x 10⁴ cells/kg.

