2.2 Study Device Information

Miltenvi Biotec. Inc.

Brand: CliniMACS® CD34 Reagent System Information

The CliniMACS® CD34 Reagent System is a medical device that is used in vitro to select and enrich specific cell populations.

The CliniMACS® CD34 Reagent System is comprised of four primary components:

- CliniMACS® CD34 Reagent: a sterile monoclonal antibody reagent specific for CD34+ cells.
- CliniMACS® plus Instrument: a software controlled instrument that processes the blood sample (cell product).
- CliniMACS® Tubing Sets: single-use, sterile, disposable tubing sets with two proprietary cell selection columns (CliniMACS® Tubing Set and CliniMACS® Tubing Set LS)
- CliniMACS® PBS/EDTA Buffer: a sterile, isotonic phosphate-buffered, 1 mM EDTA, saline solution, used as external wash and transport fluid for the in vitro preparation of blood cells

Distributor:

Corporate Headquarters Miltenyi Biotec Inc. [name]

Manufacturer:

Miltenyi Biotec GmbH, Clinical Products [name]
Bergisch Gladbach, Germany

Manufacturer Contact: Miltenyi Biotec Inc., [name]

[name] [contact] [contact]

CliniMACS $^{\circ}$ Tubing Sets (Standard and Large Scale) Standard: Up to 0.6 x 10 $^{\circ}$ CD34+ cells from up to 60 x 10 $^{\circ}$ Cells

Large Scale: 0.6-1.2 x 109 CD34+ cells from 60-120 x 109 Cells

CliniMACS® CD34 Reagent

CliniMACS® PBS/EDTA Buffer

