3.1 Inclusion Criteria

- · Participants greater than one month of age.
- Participant has a disorder that can be treated with a hematopoietic stem cell transplant
- Participant's is eligible for an allogenic HSCT as per current institutional SOP and FACT standards.
- Participant must have a related or unrelated matched or mismatched-related donor who is:
- Able to receive granulocyte colony-stimulating factor (G-CSF) and undergo apheresis either through
 placement of catheters in antecubital veins or a temporary central venous catheter OR agrees on a bone
 marrow harvest;
- Healthy as per donor selection screening (following current SOP based on standards of foundation for accreditation of cellular therapy and stem cell transplantation – FACT);
- · Willing to participate and sign consent.
- Participant or Legal Authorized Representative is able to signinformed consent (and signed assent, if applicable) for transplant.

3.2 Exclusion Criteria:

- Participant does not qualify for an allogeneic transplant due to medical screening, underlying disease, or lack of alternative donors.
- Any condition that compromises compliance with the procedures of this protocol, as judged by the principal investigator.

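### Section 5.1 gives the donor G-CSF dose in mg/kg/day but rounds it to vials of 300 or 480 micrograms in the same sentence; if the PDF also prints mg, the units must be reconciled.

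*Combined protocol and SAP*

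**What the plan says.** Section 5.1 (Mobilization Therapy for Peripheral Blood Leukapheresis) states: "Recommended dose of G-CSF is 16 mg/kg/day subcutaneously (rounded off to the nearest vial size of either 300 or 480". The sentence closes with the unit of the vial sizes, micrograms.

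The same section sets the schedule: "Donors will receive G-CSF once a day for 5 days". Leukapheresis falls on day 5, and a further dose and collection are allowed on day 6 if the cell dose requires it. It also names a second source for the regimen: "the donor will receive mobilization therapy per institutional guidelines with daily G-CSF". Those guidelines are not reproduced.

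The opening of section 5 says: "Donors will undergo standard of care procedures for mobilization and leukapheresis", and adds: "There will be no research procedures for the donor". Under section 3.1 the donor must be "Healthy as per donor selection screening" and either "Able to receive granulocyte colony-stimulating factor (G-CSF) and undergo apheresis" or willing to give a bone marrow harvest.

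**The concern.** One sentence uses two units for the same drug: milligrams for the dose per kilogram and micrograms for the vials to which that dose is rounded. A dose can only be rounded to a vial size if the two are of similar magnitude, and here they are not.

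The sentence concerns donors, who are screened as healthy, and it covers five daily doses with a possible sixth. It is the only numerical G-CSF dose in the available text, so a reader cannot resolve the conflict from elsewhere in the protocol. What is at stake is the correctness of a dosing sentence, not any statistical property of the trial.

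**Working it through.** **Inputs, all from section 5.1**

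- Dose per kilogram as it reads in the available text: 16 mg/kg/day.
- Vial sizes: 300 and 480 micrograms, that is 0.300 mg and 0.480 mg.
- Donor weight: not given in the documents and not needed, because the check can be done per kilogram.

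The plan gives no vial count or total dose, so there is no stated result to reproduce. The check is whether the two halves of the sentence fit together.

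**Step 1: common unit.** 16 mg/kg × 1,000 micrograms/mg = 16,000 micrograms/kg.

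**Step 2: vials per kilogram per day.** Dose per kg ÷ vial content:

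- 300 microgram vial: 16,000 ÷ 300 = 53.3 vials per kg.
- 480 microgram vial: 16,000 ÷ 480 = 33.3 vials per kg.

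**Step 3: the weight at which one vial is the whole daily dose.** Vial content ÷ dose per kg:

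- 300 microgram vial: 0.300 ÷ 16 = 0.01875 kg.
- 480 microgram vial: 0.480 ÷ 16 = 0.030 kg.

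No donor weighs 19 to 30 grams, so the literal dose and the vial rounding are incompatible at any real weight. Steps 2 and 3 restate one fact, the 1,000-fold difference between the units. They do not estimate what any donor would receive.

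**Step 4: does other text settle the unit?** G-CSF is also mentioned in the eligibility criteria (synopsis and section 3.1) and in the background on mobilized cells (section 2.1), each time without a dose. Section 5 defers to standard of care without figures. Section 6.3 appears in the table of contents but was not in the text available for review. Nothing that was available resolves the conflict.

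**Step 5: could the unit be a conversion error?** There are signs both ways.

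- For: the extracted text damages notation elsewhere. Section 2.2 shows "Large Scale: 0.6-1.2 x 109 CD34+ cells from 60-120 x 109 Cells", where a power of ten has lost its superscript. The line above it, for the standard tubing set, has a degree symbol where the exponent should be. Section 8.1 shows the micro sign in two different forms.
- Against: the micro sign survives later in this same sentence and in section 8.1, and no clear case was found of a micro sign turned into the letter m.

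An error in conversion is possible but not shown. Only the PDF can decide it.

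**The case against.** The strongest objection is that this may not be a defect of the plan. It turns on a single character in text with known conversion damage, and such damage does not count against the sponsor. That stands as a reason to make the finding conditional and to check the PDF first. It is not a reason to drop the point, since the unit reads plainly as mg while the micro sign is intact a few words later.

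The second objection is weight. The dose is labelled as recommended, control is assigned to institutional guidelines and standard of care, and anyone handling 300 or 480 microgram vials would notice the mismatch. Donors who give marrow are not covered by the sentence at all. All of this is true and keeps the practical risk low; a lower rating could be defended. It does not make the sentence coherent, and the guidelines that might correct it are not in the document.

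The third objection is that the vial counts look alarming while adding nothing beyond the factor of 1,000. That is fair, and they should not be read as an exposure estimate.

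**Conclusion.** The concern holds, conditional on the PDF. In the available text, section 5.1 contradicts itself: the dose per kilogram and the vial sizes differ in unit by a factor of 1,000, and the rounding instruction cannot be applied to the dose as written. If the PDF prints mg, a dosing sentence for healthy donors is wrong as it stands and should be corrected. If the PDF prints a micro sign there, the finding falls away.

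The conclusion rests on unit arithmetic alone, with no assumed donor weight and no outside source. Confidence is medium because of the conversion question. The finding does not touch the primary or secondary endpoints, the sample of 30, the graft-failure boundary or the analysis, and it makes no judgement on which figure or unit is right.

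**What to change.** 1. Compare this sentence in section 5.1 with the source PDF. If the PDF does not print mg, no change is needed.
2. If it does, the sponsor should reconcile the dose per kilogram and its unit with the vial sizes and with the institutional mobilization guideline that section 5.1 refers to only in general terms.
3. Correct the sentence through a protocol modification submitted to the IRB, as section 11.1 requires for any change.

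The cost is one check of the PDF, one check of the guideline and, if confirmed, a short wording correction with IRB review. Design, endpoints, stopping rules and analysis stay as they are. The choice of dose, unit and rounding rule belongs to the responsible clinicians and is not proposed here.

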5.2 Donor Follow-up

Donors will be followed per institution guidelines following FACT standards of care.

6 INVESTIGATIONAL PROCEDURE INFORMATION

6.1 Investigational Procedure

CD34+ Selection

CD34+ cell selection will be performed according to procedures given in the CliniMACS Users Operating Manual and institution SOPs. The processing will be performed at the Stanford BMT Cellular Therapeutics & Transplantation Laboratory at the Stanford University Medical Center.

The target cell doses will be $\ge 20 \times 10^6$ CD34+ cells/kg. A minimum dose of $\ge 5 \times 10^6$ CD34+ cells/kg will be acceptable. The target T cell dose will be $\le 3 \times 10^4$ CD3+ cells/kg.

The stem cells will be infused via central venous line into the recipient.

If > 20 x 10^6 CD34+ cells/kg are available, then 20 x 10^6 /kg will be infused and the remainder will be cryopreserved in aliquots of 5 x 10^6 CD34+ cells/kg.

Additional cell doses may be cryopreserved for future use.

6.2 Release of product for transplant

Sterility (routine USP culture for bacteria and fungi), endotoxin testing, gram stain, and viability studies will be performed in addition to the cell immunophenotyping. We already have experience with all of these procedures in other protocols at this institution (A Feasibility Trial of Post-Transplant Infusion of Allogeneic Regulatory T Cells Simultaneously with Allogeneic Conventional T Cells in Patients with Hematologic Malignancies undergoing Allogeneic Myeloablative Hematopoietic Cell Transplantation from Haploidentical Related Donors) and through pediatric stem cell transplant eIND and eIDEs submitted from this institution.

Viability, gram stain and endotoxin testing will be done prior to the release of the product for infusion. If the viability is \geq 70%, the Gram stain is negative, and the CD34+ cell and CD3+ cell doses meet the criteria, the product will be released for infusion (target cell doses will be \geq 20 x 10⁶ CD34+ cells/kg. The target T cell dose will be \leq 3 x10⁴ CD3+ cells/kg.)

If the culture becomes positive, appropriate antibiotics, per institutional protocols, will be administered to the recipient. The donor will undergo a clinical evaluation for infection and the reagents (including the aliquoted reagents) and procedures will be tested and reviewed to try to identify the source. If the gram stain is positive, the cells will be cryopreserved until the culture results are back, and the donor will undergo another leukapheresis providing he or she has no clinical evidence of infection.

All donor apheresis collections will be assessed as follows:

- Cell count by impedance counter (Coulter Z1)
- Viability by Propidium Iodide (PI) exclusion (flow cytometric assay) with target viability ≥70%,
- Sterility in accordance with 21 CFR 610.12 using Fluid Thioglycollate medium and Tryptic Soy Broth 14-day cultures
- Phenotypic analysis by flow cytometry for cell surface expression of CD34 and CD3

Final Products for infusion, including CD34 selected cells and CD3 fractions will be assessed prior to cryopreservation as follows:

- a) Cell count by hemacytometer as per SCTT current SOP
- b) Viability by Propidium Iodide (PI) exclusion (flow cytometric assay)
- c) Sterility in accordance with 21 CFR 610.12 using FTM and TSB 14-day cultures as per current SCTT current SOP
- d) Phenotypic analysis by flow cytometry for cell surface expression of CD34 and CD3

e) Endotoxin testing post-selection on each graft product as per SCTT current SOP

6.4 Agent Accountability

All quality validation will be checked at the Stanford BMT Cellular Therapeutics & Transplantation Laboratory at Stanford University Medical Center. The SCTT also has SOPs for cell sorting of PBSC and BM grafts to ensure consistent efficacy of the process. Cross reference letters are issued by the vendor, as per FDA guidelines, to notify dispensation of all supplies needed for the cell sorting.

All Reagents and materials are accounted for as per an approved Investigational New Drug (IND) application or Investigational Device Exemption (IDE) FDA guideline.

7 DOSE MODIFICATIONS

None anticipated. These are part of transplant issues but not specific to the use of the investigational device (CliniMACS® System).

8 ADVERSE EVENTS AND REPORTING PROCEDURES

8.1 Potential Adverse Events

Risk of contamination of the cell preparation with biologic or other foreign material. The sterility of system components that contact the cell sample and the detailed processing steps are designed to minimize potential contamination.

Significant animal and human studies have been done using these super-paramagnetic beads which are small in size (\sim 50 nm in diameter) and are composed of iron oxide and dextran conjugated to murine monoclonal antibodies. These magnetic particles form a stable colloidal suspension and do not precipitate or aggregate in magnetic fields. The concentration of the conjugate is equivalent to 22 μ g of antibody protein per ml of reagent, 800 μ g/ml of dextran and 800 μ g/ml of iron. Detailed toxicity studies have been undertaken to assess the safety of the antibody reagent when delivered to monkeys and rabbits in dosages significantly greater than the projected maximum dosage anticipated in clinical use (CliniMACS® Investigator brochure). There have been more than 100 separations for clinical use of the CliniMACS® system.

Reaction to CliniMACS® reagent - (murine monoclonal antibody is conjugated to an iron- dextran moiety. The iron dextran exposure from a single CliniMACS® separation is ~0.5 mg and less than 1 mg dextran.

The other reagent is the murine monoclonal antibody in which there is a risk of an anaphylactic reaction. The anti-CD34 monoclonal antibody, AC101 has been tested for safety in conformance with US standards. Systemic reactions appear related to the dose and rapidity of administration. Therapeutic levels (for cancer therapy or prevention of graft rejection) of mAb appear to be in the range of 2.5-5 mg/ml. The most commonly reported side effects have been myalgia, arthralgia, and flu-like symptoms. The CliniMACS® system results in the administration of a maximum of <15µg of antibody, 100x lower than therapeutic levels. Furthermore, studies have shown that the levels of antibody used in the CliniMACS® system do not induce complement activation in vitro.

8.2 Adverse Event Reporting

Recipients of allogeneic hematopoietic cell transplantation face significant risks. The risk of treatment related morbidity and mortality following allogeneic transplant is related to the underlying disease, disease status at the time of transplant, prior therapies and other coexisting health problems. Significant risks include:

- Infection. Risks include bone marrow suppression, prolonged hospitalization, invasive procedures, prior
 exposure to micro-organisms and immunosuppressive medications for the prevention and treatment of graft
 versus host disease. Infections may be caused by bacteria, viruses, protozoa or fungus.
- Graft versus host disease. Acute GvHD can range from a mild and treatable problem to a life threatening complication. Chronic GvHD can vary from a mild to an extensive disorder affecting almost any body tissue. Chronic GvHD can negatively affect functional status and quality of life.
- Graft failure. Although rare, graft failure is a fatal complication.
- Infertility in both genders and premature menopause in women at risk.
- Relapse. All patients face a risk of relapse. The risk is highest for those patients with active or resistant disease at the time of transplantation.

Definitions used for Reporting

Adverse Event: Any untoward medical occurrence in a patient or clinical investigation subject administered a pharmaceutical product, medical treatment or procedure and which does not necessarily have to have a causal relationship with this treatment. An adverse event can therefore be any unfavorable and unintended sign (including an abnormal laboratory finding), a symptom, or disease temporally associated with the use of a medicinal product, medical treatment or procedure whether or not considered related to medicinal product or treatment.

Life Threatening Adverse Event: Any adverse event that, in the view of the investigator, places the patient at immediate risk of death from the reaction.

Unexpected Adverse Event: An adverse event, the nature or severity of which is not consistent with the applicable product information (Investigator's Brochure, product insert). For studies that do not involve investigational products or devices, an unexpected adverse event is an adverse event that is not described in the transplant medical literature or consent form.

Serious Adverse Event (SAE): Any adverse event occurring that results in any of the following outcomes: death, a life threatening adverse event, a persistent or significant disability/incapacity, a congenital anomaly, requires intervention to prevent permanent impairment or damage. Unless the Principal Investigator is using an investigational agent, s/he is not bound by the definition in Title 22 CFR. Stanford IRB definition(s) and requirements apply when applicable, Unanticipated Problems Involving Risks to Participants or Others (UPs) and Unanticipated Adverse Device Effect (UAD)

All grades 3-5 organ-related adverse events not due to the primary malignancy or pre-existing condition will be collected from day 0 through resolution of the SAE. Grade 4 infusion reactions will be reported expeditiously and as a separate listing in the FDA Annual Report.

Distinction between Serious and Severe Adverse Events: The term severe is used to describe the intensity (severity) of a specific event, for example mild, moderate or severe. The event itself however, may be of relatively minor medical significance, for example a severe headache. This is not the same as serious, which is based on the patient/event outcome and is usually associated with events that pose a threat to the patient's life or functioning. Seriousness, not severity, serves as a guide for defining regulatory obligations.

All Adverse events will be graded using the NCI Common Terminology Criteria for Adverse Events (CTCAE) version 4.3 found on the following website:

http://ctep.cancer.gov/reporting/ctc.html

The Principal Investigator (PI) or designee will assess each Adverse Event (AE) to determine whether it is expected or unexpected according to the Informed Consent, Protocol Document, or Investigator's Brochure; and its

relationship to the investigational product.

For the purpose of this study, only AE's found to be directly related to a study-mandated intervention will be captured. The following adverse events, if felt to be related to study treatment, will be captured, but not reported as SAEs:

- Hospitalization, prolongation of hospitalization, or escalation of care due to study-mandated intervention
- Disease Relapse
- Any problems with CliniMACS device during cell separation or inability to achieve CD34+ cell and CD3+ cell target doses
- Any positive culture of HSCT product
- Failure to engraft or graft rejection

All Serious Adverse Events (SAEs) will be tracked until resolution. SAEs will be collected from the time of stem cell infusion until 30 days post cell infusion. SAEs will be reported to the IRB if they meet the definition of expedited reporting per institutional regulations. All AE's and SAE will be reported at continuing renewal.

Reports (copy of faxed MedWatch) will also be sent to Miltenyi Biotec Incorporated, to the director of Regulatory Affairs and Safety Officer at [contact].

Serious Adverse events will be reported on the MedWatch form 3500a when it meets the definition of expedited FDA reporting. All deaths will be examined to determine if they are related to the use of the CliniMACS device or infusion of manipulated product. If the death is determined to be related, the event leading to the death must be reported within 24 hours of the Investigator's awareness of the event.

The following SAEs require expedited reporting (as soon as possible but within at least 7 calendar days of the investigator learning of the event):

Deaths: All deaths up to 100 days post-transplant. This includes deaths from the common and expected grade 3-4 toxicities noted below. Deaths that occur outside of Stanford will be reported within 5 working days of knowledge of the death. It must be noted that obtaining detailed information on the cause and circumstances of a death occurring at another institution can be difficult. Excludes deaths related to relapse of underlying disease, which will reported in the annual report.

All serious and unexpected toxicities defined as those toxicities not identified in the transplant literature or in the consent form and that are felt to be related to protocol-mandated procedures.

The following will not be reported as SAEs:

- Hospitalizations: Approximately 50% of allogeneic transplant recipients will be readmitted to the hospital. The
 most common indications for readmission of an allogeneic HCT recipient are fever, failure to maintain nutritional
 status and graft versus host disease. Only hospitalizations felt to be related to study mandated interventions
 should be reported as SAE's.
- Relapse of disease: Disease relapse unfortunately remains a significant problem following both autologous and allogeneic transplantation. The risk of relapse is influenced by both patient and disease variables. The risk of relapse following allogeneic transplant is extremely dependent on the disease being treated but ranges from 10% (for patients with severe aplastic anemia) to 80% (for patients with refractory acute leukemia).
- Common and expected grade 3 4 toxicities of HSCT that are well described in the transplant literature, the product inserts or stated in the consent form and do not result in death. This includes but is not limited to neutropenia, thrombocytopenia, anemia, thrombotic microangiopathy, bleeding requiring transfusions, edema, hypertension, hypotension, gastritis, mucositis, nausea, vomiting, diarrhea, hematuria, central venous catheter infections, febrile episodes, sepsis, mental status changes, insomnia, mood alterations, seizures, tremor, pain, hypoxia, pleural effusion, pneumonitis, incontinence, infertility, laboratory abnormalities, veno-occlusive disease, graft failure, cardiac arrhythmias and graft versus host disease.
- Secondary Malignancies. The occurrence of secondary malignancies and associated mortality is a known risk of cancer therapies. The occurrence of secondary malignancies will be reported in the annual report.

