Objectives	This is a prospective study to provide access to an investigational device and reagents used for progenitor cell sorting of a stem cell transplant donor graft to determine the ability of CD34+ cell selection and T Cell depletion (using the
Objectives	CliniMACS [®] device as the sole GvHD prophylaxis) to prevent severe (grade III-IV) acute GvHD in recipients of mismatched related or unrelated donor hematopoietic stem cell transplants or with borderline organ function who might not endure the often toxic side-effects of traditional post-HSCT immunosuppressive therapy.
Primary Endpoint(s)	The primary endpoint of the study is the incidence of severe (grade III/IV) acute GvHD occurring by Day +100 after transplant.
Secondary Endpoint(s)	Outcomes measures for the secondary endpoints will include: Engraftment: The incidence of primary graft failure and graft rejection will be determined. Chimerism at Day 100: The percentage of donor cells will be reported for all evaluable (without disease progression) patients. Immune recovery: The time to CD4 count >100 and > 200 and PHA≥ 10% and 30% will be calculated. Severe toxicities: The incidence of severe toxicities will be determined. This will include grade 3/4 stem cell product infusion-related toxicity. Post-transplant infections (bacterial, viral and fungal): Post-transplant infections will be described by incidence and type. Post-transplant lymphoproliferative disease (PTLD): The incidence of PTLD will be calculated. Transplant-related mortality (TRM): The incidence of TRM will be calculated at Day 100 after transplant and at one year. Disease-free survival. Overall survival: Overall survival will be estimated using the Kaplan-Meier method. Device (CliniMACS®) performance parameters: The parameters will be summarized for all products that are processed and median and ranges will be determined.
Study Design	Participants will be enrolled with alternative (mismatched/haplocompatible) related/unrelated donors or matched related/unrelated donors for an initial HSCT.
Study Centers	This is a Stanford University, Principle Investigator (PI) initiated protocol conducted at LPCH and Stanford Hospital and Clinics.
Duration of Study per Subject	Individual participants will be followed for outcomes related to the experimental device including acute and chronic GvHD and engraftment for a minimum of one year. Subsequent follow-up care will follow the standard for all transplant patients.

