1.1 Primary Objective

To determine the ability of CD34+ cell selection using the CliniMACS® device as the sole GvHD prophylaxis to prevent severe (grade III-IV) acute GVHD in recipients of alternative donors hematopoietic stem cell transplants and/or potential matched-related allogeneic SCT recipients with borderline organ function (who might not tolerate traditional post-HSCT GvHD prophylaxis without increased morbidity).

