1.2 Secondary Objectives

Assess the ability of this approach to serve as a platform for strategies to accelerate post- transplant immunological recovery.

Evaluate chimerism at day +100 (from the date of transplant graft infusion), and the rate of engraftment in recipients of CD34+ cell selected, T cell-depleted transplants from mismatched related donors.

Evaluate the rates of post-transplant occurrences, including:

- a) Graft rejection and graft failure
- b) Immune recovery
- c) Transplant-related severe toxicities
- d) Post-transplant infections
- e) CMV infection and disease
- f) EBV-related post-transplant lymphoproliferative disorder (PTLD)
- g) Relapse of malignant-diagnosis
- h) Transplant-related mortality
- i) Disease-free survival (DFS) and overall survival (OS)

Monitor device performance:

- a) Cellular composition of final product
- b) Yield of CD34+ cells
- c) CD3+ cell depletion
- d) Sterility
- e) Purity

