2.4 Study Design

This is a PI-initiated, single institution, open (no masking is used), prospective study to provide access to allogeneic graft manipulation through CliniMACS® System for qualifying candidates.

Currently, no FDA-approved method for T cell depletion exists. Recent experience with the CliniMACS® device has produced results with a 70-75% survival in children, many of whom were high-risk patients (19, 22, 36).

Patients will be enrolled with alternative (mismatched/haplocompatible) donors for an initial transplant.

The results with mismatched related or unrelated donor transplants so far justify expanding this approach to related donor recipients who have contraindications to post-transplant immunosuppression due to borderline organ function. Matched-related or unrelated donor recipients with borderline organ function will be allowed to enroll.

It is anticipated that the use of the CliniMACS® device will result in a very low risk of GvHD without the need for post-transplant immunosuppression.

This protocol will allow the use of patient-specific conditioning regimens that are available through open IRB studies in our institution or through open treatment plans from either the pediatric or adult stem cell transplant groups at Stanford University.

The follow-up schedule and affiliated data collection forms for the allogeneic recipients in this study are the standard CIBMTR data forms and procedures.

All recipients enrolled in the study and will be assessed for: neutrophil and platelet engraftment, graft rejection, serious infusion reaction, transmission of infection from HSCs infusion, EFS, TRM, acute and chronic GvHD, HSCT-related toxicities.

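### Section 8.2 makes collection of grade 3-5 organ events depend on their not being due to a pre-existing condition, so worsening of an organ already impaired at entry can go uncollected and severe toxicity can read too low

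*Combined protocol and SAP*

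**What the plan says.** Three sentences in section 8.2 bear on which organ events reach the database.

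- The general definition of an adverse event does not depend on cause: it applies "whether or not considered related to medicinal product or treatment".
- The rule for severe organ events does depend on cause: "All grades 3-5 organ-related adverse events not due to the primary malignancy or pre-existing condition will be collected from day 0", continuing through resolution.
- A later sentence is narrower still: "only AE's found to be directly related to a study-mandated intervention will be captured".

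The PI or a designee judges relationship, and section 2.4 describes the study as open.

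On the population, section 2.4 says "Matched-related or unrelated donor recipients with borderline organ function will be allowed to enroll". The primary objective in section 1.1 names "potential matched-related allogeneic SCT recipients with borderline organ function (who might not tolerate traditional post-HSCT GvHD prophylaxis without increased morbidity". The protocol title, the Synopsis and section 1.0 give the same reason for enrolment.

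On the endpoint, the Synopsis lists among the secondary endpoints that "The incidence of severe toxicities will be determined", with no limit by cause. Section 1.2(c) words the matching objective as "Transplant-related severe toxicities". Sections 2.4 and 10.1 likewise tie toxicity to the transplant.

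The protocol defines neither a pre-existing condition nor borderline organ function. It sets no baseline grade per organ and has no rule for an organ that was impaired before transplant and gets worse after it.

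**The concern.** Some recipients enter because an organ is already impaired. If that organ worsens to grade 3-5 after transplant, the event has two candidate causes, the transplant and the earlier impairment, and they may act together. Section 8.2 itself says that treatment-related morbidity after transplant depends partly on coexisting health problems. The collection rule nevertheless treats the pre-existing condition as an alternative cause and makes that judgement a condition of recording the event.

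An event that is never collected cannot be re-adjudicated. A low severe-toxicity rate among borderline-organ-function recipients could mean that they tolerated the procedure, or that their events were set aside as pre-existing, and the data could not tell the two apart. Recipients with non-malignant disease are exposed in a similar way, because the disease being transplanted is itself a pre-existing condition.

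At stake is the interpretation of a secondary safety endpoint in a group that the study was partly designed to serve.

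**Working it through.** The documents give no severe-toxicity rate, no number of recipients with borderline organ function and no calculation that depends on either, so there is no plan figure to reproduce. The check is of the text, followed by an illustration.

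**Text**

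1. *Can the rule remove events from the count?* Yes. An event attributed to a pre-existing condition falls outside the grade 3-5 collection sentence.
2. *Can it add events?* No. The effect on the recorded incidence is downward or zero.
3. *Does it reach impaired organs?* The term is not limited to the transplanted disease, so organ impairment present at entry falls within it.
4. *Does another rule recover worsening events?* Only in part. Section 8.2 requires reporting of deaths to day 100 with no exclusion for pre-existing conditions (relapse deaths go to the annual report). The halt rule in section 10.2 for unexpected toxicity of grade IV or higher by 4 weeks has no such exclusion either. Grade 3 events, and grade 4 events that are expected or occur after 4 weeks, have no equivalent protection.
5. *Would changing this sentence alone be enough?* No. The later sentence limiting capture to directly related events would still filter the count.

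**Illustration (all inputs assumed except the 30 recipients in section 12)**

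Let *p* be the true rate of grade 3-5 worsening, *f* the share attributed to the pre-existing condition, and *m* the number of borderline-organ-function recipients. The other 30 − *m* are given the same true rate, with no events removed.

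- Recorded group rate = *p*(1 − *f*)
- Recorded overall rate = [*m p*(1 − *f*) + (30 − *m*)*p*] / 30
- Chance of recording no event in the group = [1 − *p*(1 − *f*)]^*m*

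With *m* = 10:

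| *p* | *f* | Group rate | Overall rate | Chance of no recorded event |
|---|---|---|---|---|
| 30% | 0 | 30% | 30% | 0.70^10 = 2.8% |
| 30% | 25% | 22.5% | 27.5% | 0.775^10 = 7.8% |
| 30% | 50% | 15% | 25% | 0.85^10 = 19.7% |
| 50% | 0 | 50% | 50% | 0.50^10 = 0.1% |
| 50% | 25% | 37.5% | 45.8% | 0.625^10 = 0.9% |
| 50% | 50% | 25% | 41.7% | 0.75^10 = 5.6% |

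For example, the overall rate in the third row is (10 × 0.15 + 20 × 0.30)/30 = 7.5/30 = 25%.

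Over a wider range of *f*, from 25% to 75%, a true 20% is recorded as 5% to 15% and a true 50% as 12.5% to 37.5%. At *p* = 30% and *f* = 50%, the chance of no recorded event rises from 16.8% to 44.4% if *m* = 5, and from 0.5% to 8.7% if *m* = 15.

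**The case against.** The strongest reply is that the exclusion fits the objective. Sections 1.2(c), 2.4 and 10.1 all describe toxicity as related to the transplant, and an event truly caused by baseline disease does not belong in that count. This stands. A reader might infer that the exclusion is wrong in itself, or that severe toxicity *will* be understated. The documents support neither. The rule excludes events due to a pre-existing condition. It does not say that worsening of an impaired organ is excluded, and nothing shows that the investigator would misattribute such events. What remains is a gap: worsening after transplant has no rule, and the judgement is made before collection rather than after it.

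A second reply is that the borderline-organ-function group is not singled out for toxicity. This also stands in part. Section 1.1 sets prevention of severe acute GvHD as the aim for these recipients, section 12 plans no subgroup by organ function, and section 3.1 has no such eligibility criterion. It would go too far to call organ failure in this group the study's toxicity of main interest, or to speak of a planned stratum.

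Third, deaths, the grade IV halt rule, overall survival and transplant-related mortality give partial protection. They do, but they leave many non-fatal events exposed.

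Fourth, the directly-related sentence may already exclude these events, and the CIBMTR forms or study CRFs, which are not in the documents, may collect more than 8.2 requires. The first part is a reason to repair both sentences together. The second cannot be checked from the documents.

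**Conclusion.** The point holds as a gap in the collection rule. As written, section 8.2 allows worsening of an already impaired organ to go uncollected on attribution alone, in a study that enrols some recipients because of such impairment. The direction is certain (downward or none), and the effect bears most on those recipients. The size is unknown. The fall from 30% to 15% in the group, or from 30% to 25% overall, rests entirely on assumed values for the group size, the event rate and the share set aside, and is not an estimate of actual bias.

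The study has no comparator and no test or threshold on overall severe toxicity, so no stated decision rule turns on this endpoint. The point is worth acting on because the repair is cheap and the lost events cannot be recovered later.

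**What to change.** 1. In section 8.2, replace the exclusion with a rule of this kind: *From day 0 through resolution, record each grade 3-5 organ-related event whose CTCAE grade exceeds the one the recipient had in that organ before transplant. Enter attribution (transplant or graft; pre-existing condition; primary malignancy or relapse) in its own field; it does not decide whether the event is recorded.*
2. Reconcile the later sentence on directly related events so that it does not filter this count. Without this step, the first change may have no effect.
3. Report severe toxicity in two ways: all worsening events not due to the primary malignancy or relapse, and the subset attributed to the transplant. The second serves objective 1.2(c). The first shows how far the result depends on attribution. Organ failure driven by relapse stays out of both.
4. In section 12, add a descriptive row for recipients enrolled with borderline organ function, and state how they are identified.

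The cost is an edit to section 8.2, one baseline-grade field per organ, one attribution field and one table row. Pre-transplant screening may already supply the baseline grades, but the protocol refers only to institutional procedures and FACT standards, so this should be confirmed. The downsides are a few more recorded events and a possibly less favourable toxicity rate. No treatment or clinical rule changes.
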